4.3. Description of measures intended to minimize/exclude bias

4.3.1. The assignment of serial numbers to study sites

One study site is planned to be involved, and its number will consist of any two digits.

4.3.2. Assignment of a screening number

[REDACTED]

4.3.3. The inclusion of volunteers in the study, assignment of study numbers

Randomization is not used in this study.

Volunteers will be enrolled in the study sequentially according to the cohort principle, when the inclusion in each subsequent cohort is made after confirming the safety of the dose of BCD-089 used in the previous cohort (a detailed description is presented in Section “Design”).

[REDACTED]

The investigator records the screening number and study site number in the source documentation and CRF.

JSC BIOCAD maintains lists of screening and identification numbers of all volunteers enrolled in the study.

Translated from Russian to English, dated 06-Jul-2020

4.4. Description of doses and dosing regimens of the study drugs Description of the dosage form and labeling of the study drugs

4.4.1. Description of doses and dosing regimens of the study drugs

Study No. BCD-089-1 includes seven cohorts:

1. Cohort 01 - 1 volunteer to whom a single subcutaneous injection of BCD-089 at a dose of 0.06 mg/kg will be administered.
2. Cohort 02 - a maximum of 6 volunteers to whom a single subcutaneous injection of BCD-089 at a dose of 0.3 mg/kg will be administered.
3. Cohort 03 - a maximum of 6 volunteers to whom a single subcutaneous injection of BCD-089 at a dose of 0.625 mg/kg will be administered.
4. Cohort 04 - a maximum of 6 volunteers to whom a single subcutaneous injection of BCD-089 at a dose of 1.0 mg/kg will be administered.
5. Cohort 05 - a maximum of 6 volunteers to whom a single subcutaneous injection of BCD-089 at a dose of 1.6 mg/kg will be administered.
6. Cohort 06 - a maximum of 6 volunteers to whom a single subcutaneous injection of BCD-089 at a dose of 2.2 mg/kg will be administered.
7. Cohort 07 - a maximum of 6 volunteers to whom a single subcutaneous injection of BCD-089 at a dose of 2.9 mg/kg will be administered.

A guidance for preparation of the solution for injection and the table of dose calculations and administration volumes depending on the volunteer's body weight are presented in a separate manual for performing BCD-089 injections.

The inclusion of volunteers in the study is sequential. The first to participate in the study is one volunteer, representing the cohort "01", who was administered a single subcutaneous injection of BCD-089 at a dose calculated with an additional safety factor relative to the safe starting dose - 0.06 mg/kg. In the absence of grade 3-4 adverse events related to the test product, developing within the first 7 days after the injection, three volunteers are included in cohort 02. Further, the volunteer inclusion algorithm corresponds to the following general principle:

In the absence of any grade 3-4 AEs (DLT) associated with the test product within 7 days after the injection, the next cohort of three volunteers with dose escalation is included in the study - cohort 02 (cohort 03, cohort 04, etc.).

Translated from Russian to English, dated 06-Jul-2020

If grade 3-4 AEs (DLT) associated with the test product are recorded in only one volunteer in a cohort of three volunteers, three more healthy volunteers are additionally included in this cohort.

With the development of grade 3-4 AEs (DLT) associated with the test product in two of six volunteers, the dose at which this event was recorded will be taken as the maximum tolerated dose, further dose escalation will be ceased.

4.4.2. Description of the dosage form and labeling of the study drugs

Test drug: BCD-089 (JSC BIOCAD, Russia)

Pharmaceutical form: solution for injection.

Composition per mL:

Active substance: [REDACTED]

Excipients:

[REDACTED]	[REDACTED]

Manufacturer: JSC BIOCAD, Russia

Packaging:

[REDACTED]

[REDACTED]

[REDACTED]

Labeling:

[REDACTED]

[REDACTED]

[REDACTED]

[REDACTED]

[REDACTED]

Translated from Russian to English, dated 06-Jul-2020

[REDACTED]

Composition per mL:

[REDACTED]	[REDACTED]

Manufacturer: JSC BIOCAD, Russia

Shelf life: 2 years.

Storage and transportation conditions:

[REDACTED]

Translated from Russian to English, dated 06-Jul-2020

Packaging:

[Redacted text block]

Labeling:

[Redacted text block]

Translated from Russian to English, dated 06-Jul-2020

4.6. Description of sequence and duration of all study periods

4.6.1 Schedule of study visits and procedures

The schedule of visits and their conduct are similar for the volunteers in all cohorts. A 14-day screening examination and 13 subsequent visits are planned to be conducted during the study. The first day of the study is the day of the first administered of BCD-089. The subsequent visits are calculated relative to the first BCD-089 administration. The frequency and timing of the study procedures are shown in Table 7.

Table 7. Listing and frequency of investigations and clinical examinations.

Study type	Control parameters	Frequency

[REDACTED]
 
[REDACTED]
 
[REDACTED]
	
[REDACTED]
 
[REDACTED]
 
 • [REDACTED] 	
[REDACTED]

[REDACTED]
	
 • [REDACTED] 	
[REDACTED]
 
[REDACTED]
 
[REDACTED]
 
[REDACTED]
 
[REDACTED]
 
[REDACTED]
 
[REDACTED]
 
[REDACTED]
 
[REDACTED]

[REDACTED]
 
[REDACTED]
	
 • [REDACTED] 	
[REDACTED]

[REDACTED]
 
[REDACTED]
	
 • [REDACTED] 	
[REDACTED]
 
[REDACTED]

Translated from Russian to English, dated 06-Jul-2020

Study type	Control parameters	Frequency

[REDACTED]
	
[REDACTED]
 
 [REDACTED] 	
[REDACTED]

[REDACTED]
	
 [REDACTED] 	
[REDACTED]

[REDACTED]
	
 [REDACTED] 	
[REDACTED]

[REDACTED]
	
 [REDACTED] 	
[REDACTED]

[REDACTED]
	
[REDACTED]
 
 [REDACTED] 	
[REDACTED]

[REDACTED]
	
 [REDACTED] 	
[REDACTED]

Translated from Russian to English, dated 06-Jul-2020

Table 9. Study flowchart.

Visit number	screening	1	2	3	4	5	6	7	8	9	10	11	12	13
Visit		Day 1	Day 2	Day 3	Day 4	Day 5	Day 6	Day 8	Day 11	Day 15	Day 22	Day 29	Day 50	Day 71
Day from the first injection	-14	0	1	2	3	4	5	7	10	14	21	28	49	70
Signing the Informed Consent Form	+													
Clinical and demographic data collection	+													
Assessment of vital signs	+	+ ²						+		+	+	+	+	+
Height measurement	+													
Body weight measurement	+	+												
Physical examination	+	+						+		+	+	+	+	+
Chest photofluorography	+													
Pain assessment using VAS		+	+											
Complete blood count	+							+		+		+		+
	■	■	■	■	■	■	■	■	■	■	■	■	■	■
	■	■	■	■	■	■	■	■	■	■	■	■	■	■

² On day 1, the assessment of vital signs is performed prior to administration of the drug and 1 hour after it.

Translated from Russian to English, dated 06-Jul-2020

Visit number	screening	1	2	3	4	5	6	7	8	9	10	11	12	13
Visit		Day 1	Day 2	Day 3	Day 4	Day 5	Day 6	Day 8	Day 11	Day 15	Day 22	Day 29	Day 50	Day 71
Day from the first injection	-14	0	1	2	3	4	5	7	10	14	21	28	49	70
	■	■	■	■	■	■	■	■	■	■	■	■	■	■
	■	■	■	■	■	■	■	■	■	■	■	■	■	■
Blood chemistry test	+							+		+		+		+
Blood tests for infection markers	+													
Urinalysis	+							+						+
Alcohol breath test	+													
Urine drug test (psychotropic drugs, psychoactive medications)	+													
ECG	+							+						+
Study drug injection		+												
Concomitant therapy data collection	+	+	+	+	+	+	+	+	+	+	+	+	+	+
Recording of injection site reactions		+ ³	+		+			+		+		+		+

³ On Day 1, an assessment of injection site reactions is performed prior to administration of the drug and 8 hour after it.

Translated from Russian to English, dated 06-Jul-2020

Visit number	screening	1	2	3	4	5	6	7	8	9	10	11	12	13
Visit		Day 1	Day 2	Day 3	Day 4	Day 5	Day 6	Day 8	Day 11	Day 15	Day 22	Day 29	Day 50	Day 71
Day from the first injection	-14	0	1	2	3	4	5	7	10	14	21	28	49	70
AE/SAE recording	+ ⁴	+	+	+	+	+	+	+	+	+	+	+	+	+

⁴ Only SAEs should be registered at the screening.

Translated from Russian to English, dated 06-Jul-2020

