The inclusion of volunteers in the study is sequential. The first to participate in the study is one volunteer, representing the cohort “01”, who was administered a single subcutaneous injection of BCD-089 at a dose calculated with an additional safety factor relative to the safe starting dose - 0.06 mg/kg. In the absence of grade 3-4 adverse events related to the test product, developing within the first 7 days after the injection, three volunteers are included in cohort 02. Further, the volunteer inclusion algorithm corresponds to the following general principle:

In the absence of any grade 3-4 AEs (DLT) associated with the test product within 7 days after the injection, the next cohort of three volunteers with dose escalation is included in the study - cohort 02 (cohort 03, cohort 04, etc.).

If grade 3-4 AEs (DLT) associated with the test product are recorded in only one volunteer in a cohort of three volunteers, three more healthy volunteers are additionally included in this cohort.

With the development of grade 3-4 AEs (DLT) associated with the test product in two of six volunteers, the dose at which this event was recorded will be taken as the maximum tolerated dose, further dose escalation will be ceased.

Thus, dose limiting toxicity will be assessed close to the time of administration, during the first seven days after the injection. However, it is not the end of the volunteers follow-up -

Translated from Russian to English, dated 06-Jul-2020

monitoring of their condition, as well as blood sampling for the study of pharmacokinetics, pharmacodynamics, and safety, will be carried out up to 71 days from the moment of injection.

A 14-day screening examination and 13 subsequent visits are planned to be conducted during the study. The duration of the active phase of the study (from the moment of the drug injection to the final visit) is 71 days.

The volunteer will need to be in a hospital for the entire duration of the first visit procedures (during which the test drug will be administered), since at this visit multiple blood sampling for PK studies will be performed. The volunteer will be able to leave the study site 24 hours after the administration of the test drug, provided he/she feels well and all prescribed blood sampling is completed. Starting from the "Day 3" visit, the volunteer must come to the study site approximately 1 hour before the PK blood sampling.

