Due to the need for multiple blood sampling, the volunteer has to stay at the study site for the first day after the injection.

Safety and tolerability assessment

Safety and tolerability will be assessed by monitoring vital signs (blood pressure, heart rate, and body temperature), conducting periodic physical examinations, assessing the frequency and severity of local reactions, and evaluating the results of complete blood count and blood biochemistry tests, urinalysis, and electrocardiography. These parameters will be assessed over a period of 71 days after a single-dose administration of the test drug. Additionally, information about the tenderness of subcutaneous injection, evaluated by a volunteer using a 10-point visual analog scale, will be analyzed.

Pharmacokinetic assessment

Pharmacokinetic assessment will be carried out based on data on the BCD-089 concentration in the serum of healthy volunteers. Volunteers included in the study arrive at the study site on the morning of the drug administration day. A venous catheter is installed immediately before the first blood sampling (the time from the catheter placement to the first blood sampling from it should not exceed one hour). Since multiple blood sampling is carried out only during the first day after the test drug administration, the time of placement a venous catheter will be 24 hours, after which the blood is taken by venipuncture. Detailed description of blood sampling points is presented in Table 3 below.

Translated from Russian to English, dated 06-Jul-2020

Pharmacodynamics and immunogenicity assessment

Pharmacodynamics assessment will be carried out based on data on the concentrations of C-reactive protein, soluble IL-6 receptor, human IL-6 in the serum of healthy volunteers.

Table 4. Detailed description of blood sampling for CRP, sIL-6R, IL-6 testing

Visit	Sample labeling number	Blood sampling time	Acceptable window for blood sampling	Blood volume (for 3 types of analyzed substances)
[REDACTED]	[REDACTED]	[REDACTED]	[REDACTED]	[REDACTED]
[REDACTED]	[REDACTED]	[REDACTED]	[REDACTED]	[REDACTED]
[REDACTED]	[REDACTED]	[REDACTED]	[REDACTED]	[REDACTED]
[REDACTED]	[REDACTED]	[REDACTED]	[REDACTED]	[REDACTED]
[REDACTED]	[REDACTED]	[REDACTED]	[REDACTED]	[REDACTED]
[REDACTED]	[REDACTED]	[REDACTED]	[REDACTED]	[REDACTED]
[REDACTED]	[REDACTED]	[REDACTED]	[REDACTED]	[REDACTED]
[REDACTED]	[REDACTED]	[REDACTED]	[REDACTED]	[REDACTED]
[REDACTED]	[REDACTED]	[REDACTED]	[REDACTED]	[REDACTED]

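### In the legible schedule, vital signs are taken 1 h after injection and next on Day 8, and release at 24 h requires no reading

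*Combined protocol and SAP*

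**What the plan says.** Table 9 in Section 4.6.1 has a row headed "Assessment of vital signs". It is marked at screening and on Days 1, 8, 15, 22, 29, 50 and 71. The cells for Days 2, 3, 4, 5, 6 and 11 are empty. Footnote 2 fixes the Day 1 times: "On day 1, the assessment of vital signs is performed prior to administration of the drug and 1 hour after it".

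Section 4.2 keeps the volunteer in house on the dosing day: "The volunteer will need to be in a hospital for the entire duration of the first visit procedures", and "the volunteer has to stay at the study site for the first day after the injection". He may leave "24 hours after the administration of the test drug, provided he/she feels well and all prescribed blood sampling is completed". From Day 3, "the volunteer must come to the study site approximately 1 hour before the PK blood sampling".

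Section 4.2 also names vital signs first among the methods for assessing safety, over 71 days. Section 4.6.3.3 defines one set as axillary temperature, blood pressure and wrist pulse. Neither section adds times. Section 9.2 (statistical analysis methods) lists blood pressure, pulse and temperature as quantitative safety data.

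One limit governs everything below. Section 4.6.1 also says: "The frequency and timing of the study procedures are shown in Table 7". The content of Table 7 is redacted, and so are the visit descriptions in Section 4.6.2.

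**The concern.** Section 1.4 says that the product has never been given to humans. The volunteer is under the site's care for the first 24 h and comes back on each of Days 3 to 6. The legible schedule nevertheless places one post-dose vital-sign reading before Day 8. The release condition relies on how the volunteer feels and on whether the blood has been drawn.

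Two things are at stake, both modest. A change in pressure, pulse or temperature that causes no symptoms would not be measured in the days just after a first human exposure. And the analysis of these variables in Section 9.2 would have a single post-dose time point in the first week before Day 8, so it could say little about the early course.

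**Working it through.** The stated sample size comes first, because the cost depends on it. Cohort 01 has 1 volunteer, and six further cohorts have 3 each, or 6 if expanded.

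- Minimum: 1 + 6 × 3 = 19.
- Maximum: 1 + 6 × 6 = 37, which agrees with the planned maximum of 37.

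**Present schedule.** Inputs are the Table 9 row, footnote 2, and Day 8 taken as day 7 from injection (7 × 24 = 168 h).

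- Post-dose readings during the 24 h stay: 1 (at 1 h).
- From that reading to release: 24 − 1 = 23 h.
- From that reading to the next marked one: 168 − 1 = 167 h, or 167/24 ≈ 7.0 days. The window for dose-limiting toxicity is 168 h.

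**Occasions already available.** The blood-sampling grid in Section 9.1.1 has eight times between these two readings: 2, 8, 12, 24, 48, 72, 96 and 120 h. The last five fall on Days 2 to 6. The volunteer is with staff at each of them.

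**Schedule with all eight added** (1, 2, 8, 12, 24, 48, 72, 96, 120, 168 h).

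- Readings during the stay: 5 (1, 2, 8, 12, 24 h), with intervals of 1, 6, 4 and 12 h.
- Intervals from 24 h to Day 8: 24, 24, 24, 24 and 48 h. The longest is 48 h.
- If only the in-house times were added, 168 − 24 = 144 h would stay open. That is 144/167 ≈ 86% of the present gap, so Days 3 to 6 belong in the fix.

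**Cost.**

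- Extra sets: 8 × 19 = 152 to 8 × 37 = 296.
- Measuring time, assuming 3 to 5 minutes per set: 152 × 3/60 = 7.6 h to 296 × 5/60 = 24.7 h.
- Reviews, assuming 5% to 20% of sets need one: 0.05 × 152 = 7.6 to 0.20 × 296 = 59.2. At an assumed 10 minutes each, this is 1.3 to 9.9 h.
- Total: about 9 to 35 staff hours over the whole study.

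**Side effect on the adverse-event endpoint.** If one volunteer who would otherwise have no event has an incidental grade 1 finding registered, his cohort's proportion rises by 1/3 = 33 points (n = 3) or 1/6 = 17 points (n = 6).

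The intervals and counts describe how often readings are taken. They are not estimates of risk.

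**The case against.** The strongest reply is that the controlling text cannot be read. Table 7 is named as the source for frequency and timing, and Section 4.6.2 is where an observation routine or a discharge check would normally stand. Most of the risk evaluation in Section 1.4 and the cytokine-storm study are also blacked out, so a reader cannot judge when an effect would be expected. This stands as a limit on certainty. It does not remove the point. The Table 9 row and footnote 2 are unredacted and make a positive statement of times, and the blacked-out rows of Table 9 are separate from them. If Table 7 lists more readings, footnote 2 and the blank Day 2 cell disagree with it and need aligning.

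Second, there is other cover before Day 8: adverse-event recording at every visit; a Day 1 physical examination with no stated time; injection-site checks at 8 h and on Days 2 and 4; blood pressure and temperature at unscheduled visits triggered by an event; and a single-volunteer sentinel cohort at 0.06 mg/kg with a 7-day wait. This is substantial and narrows what is left to symptomless changes. Apart from the untimed examination and the sentinel wait, it responds to symptoms, reported events or local findings.

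Third, extra readings will produce incidental findings. Section 8.2.1 requires every event from grade 1 to be registered regardless of clinical significance, entry limits are narrow (systolic 100–120, diastolic 60–80 mm Hg), and there is no control arm. This is a real cost and is counted above.

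A reader might go further and infer that the trial has no in-house monitoring after 1 h, or that dose-limiting toxicities would be missed and escalation made unsafe. The documents support neither. The first would treat redacted text as absent. For the second, dose-limiting toxicity is a related grade 3–4 adverse event, such events are asked about at every visit, and no legible rule ties escalation to scheduled vital signs.

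**Conclusion.** The point holds for the legible text. Vital signs are scheduled before dosing, at 1 h and next on Day 8, a nominal gap of 167 h, and the release condition in Section 4.2 names no reading. What remains uncovered is a symptomless change in blood pressure, pulse or temperature in that interval. The Section 9.2 analysis can still be carried out, but it has little early information. This is a worthwhile, cheap safety improvement, not an error that invalidates an endpoint or a decision. Confidence is medium, because Table 7 and Section 4.6.2 may already contain some of these readings. The gap rests on nominal visit times. The staff-hour range rests on the assumed minutes and review rate.

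**What to change.** Make these changes in all cohorts, so that each is measured alike:

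1. Reword Table 9, footnote 2, so that Day 1 vital signs are taken before dosing and at 1, 2, 8 and 12 h after it.
2. Mark Day 2 (at 24 h) and Days 3, 4, 5 and 6 in the vital-signs row.
3. Add to the release condition in Section 4.2 that the 24 h blood pressure, pulse and temperature have been taken and reviewed by the investigator. No numerical threshold is proposed; the investigator's review is the decision step.
4. Bring Table 7 and Section 4.6.2 into line, or confirm that they already say this.

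The cost is 8 further sets per volunteer (152 to 296 in all), the matching case report form fields and, under the assumptions above, about 9 to 35 staff hours. No visit is added. Some incidental grade 1 excursions will need review and possibly registration. The report should therefore interpret cohort adverse-event proportions with that in mind.

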4.6.2. Description of individual study visits

[Redacted]

[Redacted]

[Redacted]

[Redacted]

Translated from Russian to English, dated 06-Jul-2020

[REDACTED]

[REDACTED]

[REDACTED]

[REDACTED]

[REDACTED]

[REDACTED]

[REDACTED]

Translated from Russian to English, dated 06-Jul-2020

[REDACTED]

[REDACTED]
[REDACTED]
[REDACTED]
[REDACTED]

[REDACTED]

[REDACTED]
[REDACTED]
[REDACTED]
[REDACTED]

[REDACTED]

[REDACTED]
[REDACTED]
[REDACTED]
[REDACTED]
[REDACTED]
[REDACTED]
[REDACTED]
[REDACTED]
[REDACTED]
[REDACTED]
[REDACTED]
[REDACTED]
[REDACTED]

[REDACTED]

[REDACTED]
[REDACTED]
[REDACTED]

Translated from Russian to English, dated 06-Jul-2020

[REDACTED]

[REDACTED]

[REDACTED]
[REDACTED]
[REDACTED]
[REDACTED]
[REDACTED]
[REDACTED]
[REDACTED]
[REDACTED]
[REDACTED]
[REDACTED]
[REDACTED]

[REDACTED]

[REDACTED]
[REDACTED]
[REDACTED]
[REDACTED]
[REDACTED]
[REDACTED]
[REDACTED]

[REDACTED]

[REDACTED]
[REDACTED]
[REDACTED]
[REDACTED]
[REDACTED]
[REDACTED]
[REDACTED]
[REDACTED]

Translated from Russian to English, dated 06-Jul-2020

[REDACTED]

[REDACTED]
[REDACTED]
[REDACTED]
[REDACTED]
[REDACTED]
[REDACTED]

[REDACTED]

[REDACTED]
[REDACTED]
[REDACTED]
[REDACTED]
[REDACTED]
[REDACTED]
[REDACTED]
[REDACTED]
[REDACTED]
[REDACTED]
[REDACTED]
[REDACTED]
[REDACTED]
[REDACTED]

4.6.3. Description of individual clinical, laboratory, and imaging assessments

4.6.3.1. Physical examination

Physical examination must include the assessment of the following organs and systems:

- Skin and visible mucous membranes (visual inspection)
- Lymph nodes (visual inspection, palpation)
- ENT organs, respiratory system (visual inspection, lung auscultation)

Translated from Russian to English, dated 06-Jul-2020

- Cardiovascular system (heart auscultation, examination of the area of the major vessels)
- GI tract assessment (visual inspection, abdomen palpation)
- Assessment of the liver size (palpation, percussion)
- Assessment of the spleen size (palpation, percussion)
- Genitourinary tract assessment (percussion over the area of the kidneys, urinary bladder)
- Nervous system (meningeal signs, focal neurologic deficits)
- Mental status examination (signs of depression, suicidal tendencies, acute psychotic disorder)

4.6.3.2. Clinical and demographic data collection, history of drug therapy

The following data on the volunteer should be recorded at the screening:

- Date of birth
- Sex
- Age
- Assessment of child-bearing potential (birth control methods use, data on sterilization if applicable)
- Collection of past medical history (infectious diseases, general disorders, surgery etc.)
- Collection of history of drug therapy: medicinal products that the volunteer had been taking within 30 days before the screening specifying the dose, dosing frequency, duration of treatment, reasons for discontinuation (if applicable)

4.6.3.3. Assessment of vital signs

Vital sign assessment includes measurement of axillary body temperature (in degrees Celsius), measurement of blood pressure (on one arm, in mmHg), pulse rate at the wrist.

